6.2 Schedule of Assessments for the one-time visits

	Healthy Control (n=75)	Long-COVID Participant (n=75)
Activity	One Time Visit	One Time Visit
Informed Consent ¹	X	X
Demographics	X	X

Randomized, Placebo-Controlled Parallel Group Clinical Trial of Nicotinamide Riboside to evaluate NAD+ Levels in Individuals with Persistent Cognitive and Physical Symptoms After COVID19 Illness ("Long-COVID") Version 1.1

Medical & COVID-19 History	X	X
Long COVID-19 symptoms assessment	-	X
SARS-CoV-2 PCR test	X	X
Height and Weight	X	X
Vital Signs	X	X
Inclusion/ Exclusion Review ⁴	X	X
SMMSE	X	X
Concomitant Medications and Supplements ⁴	X	Х
AE Reporting ^{4,5}	X	X
Office Cognitive Assessment ⁶	X	X
Neuropsychiatric Assessment ⁷	X	X
Office Functional Assessment	X	X
Blood Collection for PK and Biomarkers ⁸	X	X
Subjective cognitive concerns assessment ⁹	X	Х
Sleep Assessment ¹¹	X	X

¹No study procedures apart from the telephone pre-screening visit will be performed prior to the signing of the informed consent form (ICF). All subjects will sign an ICF prior to undergoing any study tests or procedures.

Randomized, Placebo-Controlled Parallel Group Clinical Trial of Nicotinamide Riboside to evaluate NAD+ Levels in Individuals with Persistent Cognitive and Physical Symptoms After COVID19 Illness ("Long-COVID") Version 1.1

²After initial assessment of medical history during the screening period, updated medical history will be collected in subsequent visits.

³Safety labs include Hematology (CBC with differential), Complete Chemistry Panel, Liver Function Tests, B12 and TSH, as well as a pregnancy test to women of childbearing potential.

⁴These procedures can take place virtually via Zoom videoconference if necessary.

⁹ECog ¹⁰IPAQ

Randomized, Placebo-Controlled Parallel Group Clinical Trial of Nicotinamide Riboside to evaluate NAD+ Levels in Individuals with Persistent Cognitive and Physical Symptoms After COVID19 Illness ("Long-COVID") Version 1.1

⁵All adverse events that occur AFTER signing consent form until the end of the follow up visit will be included.

⁶Including D-KEFS Verbal Fluency, Trail Making Test, RBANS, WAIS-IV Digit Span Backwards, BRIEF-A, CPT.

⁷Including BDI, BAI, PCL-C

⁸Including collection of dried blood spot samples

¹¹Pittsburgh Sleep Quality Index

¹²Fitbit Charge 4 Wearable Device

6.2.1 Screening/Lead-In Visit (Week 0)

The screening procedures will determine the subject's eligibility for the study and will take approximately 3 hours.

The following procedures will take place at the Screening/Lead-In visit:

- Obtain written informed consent from the subject.
- Obtain demographics and medical history, including assessment of COVID-19 symptoms
- Complete SARS-CoV-2 PCR test
- Safety Labs
- Perform physical and neurological examination
- Measure Vital Signs
- Measure height and weight
- Review and document concomitant medications, supplements, and therapies
- Administer the MMSE
- Provide Fitbit
- Administer questionnaires about neuropsychiatric symptoms, sleep, physical activity, and others.
- Dispense PBO

6.2.1.1 Screen Failures

Any subject who signs consent will be considered enrolled in the study. If a subject fails screening, at a minimum, the following information should be captured and entered into the Electronic Data System (EDC).

- Inclusion/Exclusion Criteria
- Demographics
- Reason for screen failures

6.2.2 Baseline Visit (Week 2)

The following procedures will be performed and will take approximately 4-5 hours depending on participation in the MRI sub-study. If the subject has elected to participate in the MRI sub-study, the visit may occur over multiple days as long as all tasks are completed during the study visit window.

- Measure Vital Signs
- Blood draw and a collect dried blood spot sample for biomarker analysis
- Assess study supplement compliance
- Assess COVID-19 related symptoms
- Administer cognitive assessments
- Administer questionnaires about neuropsychiatric symptoms, sleep, physical activity and others
- Assess and document AEs and changes to medical history¹
- Review and document concomitant medications, supplements, and therapies¹
- Dispense study supplement or PBO¹
- Perform optional MRI scan
- Reassess inclusion and exclusion criteria¹

6.2.3 Follow Up Visits (Weeks 7, 12 and 17)

These visits will take place every 5 weeks (± 2 days) following Baseline.

Randomized, Placebo-Controlled Parallel Group Clinical Trial of Nicotinamide Riboside to evaluate NAD+ Levels in Individuals with Persistent Cognitive and Physical Symptoms After COVID19 Illness ("Long-COVID")
Version 1.1

¹These procedures can take place virtually via Zoom videoconference if necessary.

- Review and document concomitant medications, supplements, and therapies¹
- Assess COVID-19 related symptoms
- Perform physical assessments
- Perform physical and neurological examination
- Measure vital signs
- Dispense study supplement or PBO¹
- Assess study supplement compliance
- Administer battery of cognitive assessments (only week 12)
- Administer questionnaires about neuropsychiatric symptoms, sleep, physical activity and others
- Blood draw and a collect dried blood spot sample for biomarker analysis
- Assess and document adverse events (AEs) and changes to medical history¹

6.2.4 Final study visit

This visit will take place at Week 22.

- Measure Vital Signs
- Perform physical and neurological examination
- Blood draw and a collect dried blood spot sample for biomarker analysis
- Assess study supplement compliance
- Assess COVID-19 related symptoms
- Administer cognitive assessments
- Administer questionnaires about neuropsychiatric symptoms, sleep, physical activity and others
- Assess and document AEs and changes to medical history¹
- Review and document concomitant medications, supplements, and therapies¹
- Perform physical assessments
- Perform optional MRI scan

6.2.5 Early Termination Visit

If the subject withdraws from the study before completion of all study visits, they will be invited to participate in an Early Termination Visit within 7 days of stopping treatment.

- Measure Vital Signs
- Perform physical and neurological examination
- Blood draw and a collect dried blood spot sample for biomarker analysis
- Assess study supplement compliance
- Assess COVID-19 related symptoms
- Administer cognitive assessments
- Administer questionnaires about neuropsychiatric symptoms, sleep, physical activity, and others
- Assess and document AEs and changes to medical history¹
- Review and document concomitant medications, supplements, and therapies¹
- Perform optional MRI scan

Randomized, Placebo-Controlled Parallel Group Clinical Trial of Nicotinamide Riboside to evaluate NAD+ Levels in Individuals with Persistent Cognitive and Physical Symptoms After COVID19 Illness ("Long-COVID")

Version 1.1

¹These procedures can take place virtually via Zoom videoconference if necessary.

¹These procedures can take place virtually via Zoom videoconference if necessary.

¹These procedures can take place virtually via Zoom videoconference if necessary.

6.2.6 HC One Time Visit

Healthy control subjects will only complete one visit.

- Obtain written informed consent from the subject.
- Obtain demographics and medical history, including assessment of COVID-19 symptoms
- Complete SARS-CoV-2 PCR test or a rapid antigen test
- Measure Vital Signs
- Measure height and weight
- Administer the MMSE
- Administer questionnaires about neuropsychiatric symptoms, sleep, physical activity and others.
- Blood draw and a collect dried blood spot sample for biomarker analysis
- Administer cognitive assessments
- Perform MRI scan (if participant is ≤65 years of age)

6.2.7 Long-COVID One Time Visit

Long-COVID participants will only complete one visit.

- Obtain written informed consent from the subject.
- Obtain demographics and medical history, including assessment of COVID-19 symptoms
- Complete SARS-CoV-2 PCR test or a rapid antigen test
- Measure Vital Signs
- Measure height and weight
- Administer the MMSE
- Administer questionnaires about neuropsychiatric symptoms, sleep, physical activity and others.
- Blood draw and a collect dried blood spot sample for biomarker analysis
- Administer cognitive assessments
- Perform MRI scan (if participant is 65 years of age or younger)

6.2.8 Protocol Deviations

A protocol deviation is any noncompliance with the current clinical trial protocol. The noncompliance may be on the part of the subject, the PI, or the study staff. As a result of deviations, corrective actions will be developed by the PI and implemented promptly. All deviations from the protocol must be addressed in the subject's documents. Protocol deviations will be sent to the IRB per their guidelines and entered in the Protocol Deviations Log in the EDC System.

6.2.9 Missed Visits and Procedures

Missed visits and any procedures not performed (not attempted) for reasons other than illness or injury will be reported as a protocol deviation. Procedures or visits not performed due to illness, injury, or disability, including procedures that were attempted but failed (i.e., weight unable to be obtained due to subject immobility) will not be reported as protocol deviations. Participants who are unable to attend their visit within the approved 3-day window will receive overnight-shipped extension supplements before their original supply runs out. This allows them to maintain their supplement regimen until they can come in for their visit. We will confirm their mailing address before we send the supplement and provide the tracking number. Signature will be required upon delivery. We will also contact them on the date that they receive the supplement to confirm that it arrived in perfect condition.

7 CLINICAL ASSESSMENTS AND OUTCOME MEASURES

Randomized, Placebo-Controlled Parallel Group Clinical Trial of Nicotinamide Riboside to evaluate NAD+ Levels in Individuals with Persistent Cognitive and Physical Symptoms After COVID19 Illness ("Long-COVID")

Version 1.1

7.1 Clinical Variables

Assessments will be performed at designated time-points throughout the study for clinical evaluation. In addition to the assessments evaluated below, subjects will provide information on their demographics, past medical and COVID-19 history, family history, and concomitant medication usage.

7.1.1 Safety Measures

7.1.1.1 Vital Signs, Height, Weight

Vital signs, including systolic and diastolic blood pressure, pulse rate (radial artery)/minute, respiratory rate/minute, and temperature will be assessed at specified visits. Verbal weight may be documented for those subjects utilizing a wheelchair.

7.1.1.2 Clinical Laboratory Assessments

Study participants in the clinical trial will be asked to provide approximately 20 mL of blood for safety lab analysis at screening. The participant will have his or her whole blood collected by either a nurse or phlebotomist from a peripheral vein. Blood will be handled, processed, and analyzed in accordance with regulations set forth by the American Society for Clinical Pathology and the College of American Pathologists.

The investigator may order additional testing, if thought to be necessary, to further assess an adverse event (AE).

7.1.1.3 Adverse Events

Once the informed consent form has been signed by the subject, inquiry about all adverse events (AEs) will be performed at each study visit. The AE grading system being used will be the CTCAE protocol.

7.1.2 Clinical Assessments

7.1.2.1 Neuropsychiatric and Functional Assessments

7.1.2.1.1 Beck Anxiety Inventory (BAI)

The Beck Anxiety Inventory³¹ (BAI) is a 21-item, self-administered questionnaire that measures the presence and severity of anxiety in psychiatric populations. It was constructed to avoid confounds due to comorbidity of depression, and it has been found to be highly valid, reliable, and consistent²³. The BAI lists 21 common symptoms of anxiety and asks the subject to rate the severity with which they experience each symptom (not at all, mildly, moderately, or severely). Scores of 0-21, 21-35, or 36-63 indicate low, moderate, or severe anxiety, respectively.

7.1.2.1.2 Beck Depression Inventory (BDI)

The Beck Depression Inventory³² (BDI) is a widely used assessment of depression severity used in clinical and research settings. It is a 21-item, self-administered rating inventory with a mean internal consistency of 0.86. The BDI ranks responses to several domains of depression, including mood changes, guilt, self-image, suicidality, affect, and apathy on a scale from 0 to 3 and provides an assessment of the level of depression, spanning minimal to mild to moderate to severe depression.

7.1.2.1.3 Post Traumatic Stress Disorder Checklist – Civilian (PCL-C)

Randomized, Placebo-Controlled Parallel Group Clinical Trial of Nicotinamide Riboside to evaluate NAD+ Levels in Individuals with Persistent Cognitive and Physical Symptoms After COVID19 Illness ("Long-COVID")

Version 1.1

The Post Traumatic Stress Disorder Checklist – Civilian (PCL-C)³⁰ is a standardized self-report measure of post-traumatic stress disorder (PTSD) that was designed to be applied to any traumatic event. The PCL-C is comprised of 17 items that correspond to key symptoms of PTSD as established by the Diagnostic and Statistical Manual of Mental Disorders (DSM).

7.1.2.1.4 Behavior Rating Inventory of Executive Function (BRIEF-A)

The Behavior Rating Inventory of Executive Functioning (BRIEF-A)²⁸ is a standardized rating scale to assess self-regulation and executive function in everyday behaviors. It is a 75-item scale including a Behavioral Regulation Index consisting of inhibition, shifting, emotional control, and self-monitoring scales and a Metacognition Index consisting of initiation, working memory, planning/organization, task monitoring, and organization of material scales. This study will only use the BRIEF-A self and not the informant report.

7.1.2.1.5 Pittsburgh Sleep Quality Index

The Pittsburgh Sleep Quality Index³⁴ is a self-report questionnaire that assesses sleep quality over a 1-month time interval. It consists of 19 individual items that are usually completed between 5 to 10 minutes.

7.1.2.1.6 International Physical Activity Questionnaire (IPAQ)

The International Physical Activity Questionnaire³⁵ is a self-reported measure of physical activity that can be administered by telephone interview or self-administration. The IPAQ collects information on time spent walking, in vigorous- and moderate-intensity activity and in sedentary activity. The IPAQ has been attributed reasonable measurement properties for monitoring population levels of physical activity among 18- to 65- years old adults in diverse settings.

7.1.2.2 Neurocognitive Assessments

7.1.2.2.1 Mini-Mental State Examination (MMSE)

The Mini-Mental State Examination (MMSE)²² is a widely used cognitive screening measure that includes items that measure orientation, attention, memory, language, and visuo-spatial abilities. Scores range from 1 to 30, with scores greater than 25 being considered normal.

7.1.2.2.2 Repeatable Battery for the Assessment of Neuropsychological Status (RBANS)

The Repeatable Battery for the Assessment of Neuropsychological Status (RBANS)²⁴ is a commonly used 25-minute, standardized neurocognitive battery assessing functioning across multiple cognitive domains. It is designed to be administered repeatably, with several equivalent alternate forms available. The RBANS measures a total of five neurocognitive domains using twelve subtests: immediate memory (List Learning and Story Memory), visuospatial/constructional (Figure Copy and Line Orientation), language (Picture naming and Semantic Fluency), attention (Digit Span and Coding), and delayed memory (List Recall, List Recognition, Story Memory, and Figure Recall). The RBANS will be administered at Baseline, Week 12, and End of Study (Week 22) using alternate forms.

7.1.2.2.3 Trail Making Test (TMT)

The Trail-Making Test (TMT)²⁵ is a graphomotor letter and number-letter sequencing task that will be administered to test processing speed, mental flexibility, and set-switching. The test takes approximately 5 minutes to complete.

Randomized, Placebo-Controlled Parallel Group Clinical Trial of Nicotinamide Riboside to evaluate NAD+ Levels in Individuals with Persistent Cognitive and Physical Symptoms After COVID19 Illness ("Long-COVID")

Version 1.1

7.1.2.2.4 Wechsler Adult Intelligence Scale – 4th edition (WAIS-IV) Digit Span

Wechsler Adult Intelligence Scale – 4th edition (WAIS-IV) Digit Span²³ is a verbal measure of attention and working memory that consists of three tests: 1) digits forward, which requires repeating a string of numbers; 2) digits backwards, which requires repeating a string of numbers backwards; and 3) and digit sequencing, which requires organizing a string of numbers from lowest to highest.

7.1.2.2.5 Delis-Kaplan Executive Function System (DKEFS) Verbal Fluency

The Delis-Kaplan Executive Function System (DKEFS) Verbal Fluency²⁶ is a measure of executive functioning that is composed of three different conditions: 1) phonetic fluency, which requires listing as many words as possible that begin with a specific letter in 60 seconds; 2) semantic fluence, which requires listing as many animals as possible in 60 seconds; and 3) category switching requires switching between two semantic categories in 60 seconds.

7.1.2.2.6 Everyday Cognition Scale (ECog)

The Everyday Cognition Scale (ECog)²⁹ is a self-report questionnaire that assesses a global factor and six domain-specific factors associated with everyday function and cognition (e.g. memory, planning, organization, language, etc). The ECog has been shown to be correlated with objective neuropsychological tests.

7.1.2.2.7 Continuous Performance Test (CPT)

The Continuous Performance Test is a test of sustained attention and alertness in which subjects are presented with a string of letters²⁷. The subject is instructed to press a button every time they see an X and not to press it for any other letter. Letters are presented for five minutes. The subject is then given a brief break before continuing to the next part of the study, the AX task. In this section, the subject is told to press the button when they see an X that follow right after an A but not when there is an X that is not preceded by an A. The subject is then presented with another five-minute block of letters. This section of the task is also a test of inhibition and executive control. Task administration will utilize Millisecond Inquisit software, a computerized stimulus presentation platform optimized for temporally precise stimuli presentation and reaction time recording of psychological assessments. The CPT will be administered at Baseline, Week 12, and End of Study (Week 22). Inquisit Web requires only a subject code and no personally identifiable information.

7.1.2.3 Physical Functioning Assessment

7.1.1.3.1 Physical and Neurological Examination

A physical and neurological examination will be performed at the Baseline visit, Visit 2, and End of Study (Week 22). The following systems will be examined: general appearance, head, eyes, ears, nose, throat, neck, chest, heart, abdomen, extremities, edema, peripheral vascular, skin and appendages, musculoskeletal, central nervous system, muscles and back. COVID-19 related symptoms will be measured using the COVID-19 checklist and the C19-YRS rehabilitation screening tool. HC and long-COVID participants will not undergo a physical and neurological examination.

7.1.2.4 Phlebotomy and collection of dried blood spot samples for Biomarkers

Subjects will provide additional blood samples for biomarker analysis from Baseline to End of Study visits, and HC and long-COVID participants during their one-time visit. Biomarker analysis will include NAD+/NADH, cytokines (e.g. IL-6), oxidative stress marker 8-OHdG), Irisin; NfL, A β 42, A β 40, tau, GFAP, UCH-L1, and other analytes. At each visit (Weeks 0-22), 20 ml (1.3 tablespoons) of blood will be collected for these analyses,

Randomized, Placebo-Controlled Parallel Group Clinical Trial of Nicotinamide Riboside to evaluate NAD+ Levels in Individuals with Persistent Cognitive and Physical Symptoms After COVID19 Illness ("Long-COVID")

Version 1.1

for a total of 120 ml (7.8 tablespoons) over the course of the study. Subjects will also provide a dry blood spot sample with a finger prick to measure the concentration of NAD+ from Baseline to End of Study visits.

7.1.2.5 Magnetic Resonance Imaging (MRI)

Subjects will be given the opportunity to participate in an optional MRI sub-study at Baseline (Week 0) and End of Study (Week 22). Subjects in the healthy control group will complete the MRI at their one-time visit. Subjects electing to participate will be asked to complete both MRIs to be part of the sub-study. Data will be collected on a 3-Tesla Siemens scanner with the following scan sequences: a high resolution T1-weighted scan, T2 FLAIR, resting state BOLD MRI, and pCASL at rest.

Resting state BOLD measures low-frequency spontaneous fluctuations in BOLD signal across time, where correlations of this spontaneous activity between brain regions are thought to reflect functional connectivity. The 10-minute rsfMRI scan will be acquired with whole-brain echo planar imaging (EPI) time series with a voxel size of 2x2x2 mm isotropic, TR/TE = 4000/30 ms, acquisition matrix = 64x64, and 40 axial slices. Subjects will be instructed to keep their eyes open throughout the duration of the scan. rsfMRI data will be processed within the FreeSurfer FS-FAST stream using standard pre-processing steps including motion correction, masking of non-brain tissue, registration to the anatomical high-res image, sampling to the surface, and surface smoothing by 5 mm. Temporal filtering to extract signals in the 0.008-0.08 Hz frequency band will be performed, followed by linear regression to factor out mean global signal, average signal from white matter, and average signal from ventricular cerebrospinal fluid (CSF) regions. To perform functional connectivity analyses, we will use a seed-based approach to examine temporal correlations between the mean time course within anatomically-defined nodes and the rest of the brain.

ASL-MRI is another indicator of brain function, quantifying regional cerebral blood flow, which in turn is linearly coupled to regional brain metabolism and neuronal activity³⁶. It is especially well suited to drug trials in which change from baseline is of prime interest. Pseudo-Continuous ASL (pCASL), which provides excellent sensitivity and temporal stability³⁷, will be used in the protocol. The single shot pCASL scan will be acquired with the following parameters: 24 cm field of view, 2x2x2 mm isotropic, TR/TE = 4300/3.2 ms, acquisition matrix = 64x64, slice thickness = 6mm, temporal bolus = 1800 ms with a 1800 ms post labeling delay. Corresponding field map scans will also be acquired to correct for blurring and signal dropout during image processing. All data processing and analysis will utilize tools available through FSL's Bayesian Inference for Arterial Spin Labeling MRI (BASIL) toolbox.

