3.2 Study Objectives

The primary objective of the study will be:

1. To measure the effect of NR vs PBO on standard assessments of cognition and subjective cognitive concerns.

The secondary clinical objectives of the study will be:

- 2. To measure the effect of NR vs PBO on neuropsychiatric symptoms;
- 3. To measure the effect of NR vs PBO on physical functioning.

The tertiary clinical objective of the study will be:

1. To elucidate how NAD+ levels, cognitive functioning, neuropsychiatric and physical symptoms, and markers of neural injury and inflammation differ between individuals with long-COVID and healthy controls.

The exploratory biomarker objectives of the study will be:

- 1. To measure the effect of NR on plasma biomarkers of metabolic target engagement and central nervous system (CNS) neural and glial integrity measurable in blood.
- 2. To measure the effects of NR on cerebral neurophysiology (in an optional sub-study) using resting state functional magnetic resonance imaging (rs-fMRI). Connectivity will be measured with rsBOLD.

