9.1 Primary analysis

For all outcomes, we will perform intention-to-treat (ITT) analysis and mixed-effects model repeated measures (MMRM). Group (NR-NR vs. PBO-NR sequence), time, and group by time interactions will be included in the MMRM as fixed effects. The study's outcomes will be the change score of ECog, RBANS, and TMT-B from baseline, and the change in NAD+ levels from baseline. We also will examine changes in the FSS, BAI, BDI, and PSQI scores. An unstructured covariance matrix will be used to account for the correlation of repeated measures within a participant. Age, sex, and education will be included in the models as covariates.

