10.1.1 Potential Risks

Nicotinamide Riboside: Nicotinamide riboside is well-tolerated in patients, with few adverse events reported in a minority (3.3%) of patients¹⁶:

- Mild nausea
- Mild skin rash
- Mild flushing/hot flashes
- Mild leg cramps
- Increased bruising

None of the reported adverse events led to discontinuation of NR during its intervention period.

Phlebotomy: The risks associated with having blood drawn, including the dried blood spot from the finger prick, include bruising and local discomfort. Rarely an infection may occur at this site, and if an infection does occur it will be treated by the study physician.

Magnetic Resonance Imaging: MRI is a safe procedure for subjects who do not have metal implants or other contraindications. Individuals who have electrically, magnetically, or mechanically-activated implants (such as

Randomized, Placebo-Controlled Parallel Group Clinical Trial of Nicotinamide Riboside to evaluate NAD+ Levels in Individuals with Persistent Cognitive and Physical Symptoms After COVID19 Illness ("Long-COVID")

Version 1.1

heart pacemakers) or those who have clips on blood vessels in their brain will not be allowed to participate in the study due to risks associated with MRI scanning. The MRI will be operated in a manner accepted by the FDA. The protocol requires subjects to remain still within a relatively confined space during the scanning session, and the scanner makes loud knocking and beeping sounds as it takes images. While subjects with severe claustrophobia are excluded from the study, some subjects may find the physical confinement or noise uncomfortable. Every effort will be made to enhance each subject's comfort level, and subjects will be given earplugs to reduce discomfort due to noise. If a subject notices any discomfort while in the MRI scanner, (s)he should notify the administrator immediately. If the discomfort cannot be stopped, the scanning session will be stopped. The MRI has the potential, during normal routine use, to cause localized warming of the skin and underlying tissues. Subjects should immediately inform the study staff if they experience discomfort due to warming of the skin and the procedure will be stopped.

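### The stated resting-state nuisance regression names no motion parameters and no motion measure in group comparisons, so residual head movement could bias connectivity, chiefly in long-COVID versus recovered controls; size unknown

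*Combined protocol and SAP*

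**What the plan says.** Section 7.1.2.5 of the combined protocol and SAP processes the resting-state data in FS-FAST "using standard pre-processing steps including motion correction, masking of non-brain tissue, registration to the anatomical high-res image", then surface sampling and 5 mm smoothing. The data are next band-pass filtered to 0.008-0.08 Hz. The nuisance step comes after the filter and is worded as "followed by linear regression to factor out mean global signal, average signal from white matter, and average signal from ventricular cerebrospinal fluid (CSF) regions". For the connectivity analysis, "we will use a seed-based approach to examine temporal correlations between the mean time course within anatomically-defined nodes and the rest of the brain".

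Other relevant places:

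- Section 3.2 lists the effect of NR on cerebral neurophysiology as an exploratory objective in an optional sub-study: "Connectivity will be measured with rsBOLD".
- Section 4.2 requires scans of 50 healthy controls and 50 one-time long-COVID participants aged 65 or under. In the trial it allows 24 completers of the repeat scan and 50 further baseline scans.
- Section 9.1 says: "Age, sex, and education will be included in the models as covariates". Section 9 names no MRI outcome and gives no group-level imaging model.
- Section 10.1.1 says: "The protocol requires subjects to remain still within a relatively confined space during the scanning session". It sets no numerical limit on movement.

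The MRI text, the MRI risk text and the statistics section mention no motion regressor, volume censoring, motion-based scan exclusion or subject-level motion covariate.

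**The concern.** Realignment puts the volumes back in register. It does not remove the intensity changes that movement causes. If a seed and a target region share such a change, their correlation rises even though the underlying connectivity is the same.

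This matters most where groups are not randomised. Under Section 4.1.1, long-COVID participants must have at least two ongoing symptoms from a list that includes musculoskeletal or chest pain, shortness of breath, weakness and tingling, while controls must have recovered fully. Some of these symptoms could plausibly affect how still a person lies, so movement may be linked to group. A difference in movement could then be read as a feature of long-COVID.

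A pre-post reading of the repeat-scan sub-study has a related weakness: people may move less at the second scan because the scanner is familiar.

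**Working it through.** **Text check.** The plan gives no sample size, power or effect size for connectivity, so there is no figure of its own to reproduce. Section 7.1.2.5 treats motion correction and nuisance regression as separate steps. The pre-processing list is open-ended ("standard pre-processing steps including motion correction, masking of non-brain tissue" follows the word for a partial list). The nuisance regression names exactly three signals.

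**Group sizes (Section 4.2).** The one-time visits give 50 long-COVID v 50 controls. If trial baseline scans are pooled in, long-COVID rises to 50 + 24 + 50 = 124, so 124 v 50.

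**Degrees of freedom (Section 7.1.2.5).**
- 10 min at TR 4 s: 600 / 4 = 150 volumes.
- Frequency spacing is 1/600 Hz. The band 0.008-0.08 Hz covers 4.8 to 48 spacings, so bins 5 to 48, which is 44 bins or 88 df.
- After three regressors: 88 - 3 = 85. After six more: 85 - 6 = 79.

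**Size of the bias (all artefact inputs are assumptions).** Let f be the share of variance in seed and target that is shared movement artefact left after the stated regression. Then

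observed r = r_true(1 - f) + f.

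Take r_true = 0.2, between-person SD 0.15, f = 5% in controls, and a two-sided 5% test. The variance of one person's observed r is about

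[(1 - f) x 0.15]^2 + (1 - r^2)^2 / 85.

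Controls: r = 0.2 x 0.95 + 0.05 = 0.240; SD = sqrt(0.1425^2 + 0.9424^2/85) = 0.175.

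Long-COVID at f = 10%: r = 0.2 x 0.90 + 0.10 = 0.280; SD = 0.168. The spurious difference is 0.040. For 50 v 50 the standard error is sqrt(0.175^2/50 + 0.168^2/50) = 0.0343, so the shift is 0.040/0.0343 = 1.16 standard errors. The false-positive rate is Phi(1.16 - 1.96) + Phi(-1.16 - 1.96), about 21%.

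The same steps for other shares give:

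| Long-COVID f (controls 5%) | Spurious difference in r | 50 v 50 | 124 v 50 |
|---|---|---|---|
| 5% | 0 | 5% | 5% |
| 6% | 0.008 | 5.6% | 5.9% |
| 7% | 0.016 | 7.5% | 8.5% |
| 8% | 0.024 | 11% | 13% |
| 10% | 0.040 | 21% | 28% |
| 15% | 0.080 | 66% | 80% |

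Simulations with the same r, SD and artefact shares gave 22 to 23% (50 v 50) and 28 to 30% (124 v 50) at f = 10%, and 64 to 65% and 80 to 82% at f = 15%. They agree with the approximation.

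**Randomised sub-study.** With 24 completers, taken as 12 v 12 for illustration, a 5% v 10% gap between arms gives about 9%.

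**The case against.** The strongest reply is that this is a matter of reporting detail in an exploratory pipeline. Several parts of it stand.

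- **A reader might infer that motion is not handled, or that the realignment parameters will not be used.** The documents do not support that. Motion correction is specified, the pre-processing list is open-ended, and no group-level imaging model is written from which a covariate could be said to be missing. What can be said is that the plan does not state these uses.
- **The residual share may be small.** Artefact shared across the brain is what global-signal regression targets. No figure in the documents supports any particular gap between groups, and a gap of one or two percentage points leaves the error rate close to nominal.
- **Symptoms need not imply movement.** Any two symptoms qualify, so a participant with fatigue and hair loss would be eligible.
- **A reader might infer that a reported NR effect on connectivity would be a motion artefact.** That goes too far. Between randomised arms, familiarity with the scanner is balanced in expectation. By Week 22 both arms are on NR (Section 3.1 and the schema in Section 5.3), so a pooled pre-post comparison lacks a placebo control whatever is done about motion.
- **The comparison with controls is implied, not stated.** The tertiary objective in Section 3.2 does not name connectivity. The required control scans are what imply the comparison, and no test is specified for it.

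One part does not stand. The nuisance regression is more than an unfilled detail: it is a specific model of three signals. A team that followed it as written would leave out regressors that its own realignment step produces.

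**Conclusion.** The point holds as a modest, avoidable weakness in an exploratory analysis. Followed as written, the nuisance model may leave residual motion confounding, mainly in long-COVID versus recovered controls and secondarily in any pre-post reading of the repeat scans.

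Its size cannot be determined from the documents. The error rates run from close to nominal to severe, and they depend almost entirely on the assumed gap in residual artefact between groups. They also rest on the assumed true correlation and between-person SD, a single seed-target pair, and an artefact shared equally by both regions. They show how sensitive the comparison is and do not predict what this trial will find. The plan gives no reason to prefer the upper end.

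Nor should a reader assume that motion regression would restore the nominal error rate. That depends on how far real movement artefact follows the realignment parameters linearly, which nothing here tests.

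**What to change.** In Section 7.1.2.5:

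1. Add the six realignment parameters from the planned motion-correction step to the nuisance regression, filtered to the same 0.008-0.08 Hz band as the data.
2. Report mean framewise displacement by group, and by visit for repeat scans.
3. Repeat the long-COVID versus control comparison adjusted for mean framewise displacement, as a sensitivity analysis. It should not be the main result: if illness itself causes movement, the adjustment could remove part of a real difference.

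The cost is a few sentences and no new data. Six of about 85 in-band degrees of freedom are lost per scan (7%). Under the assumptions above, a control's SD rises from 0.175 to sqrt(0.1425^2 + 0.9424^2/79) = 0.178, a little over 1%. Frame censoring is a further option, but it would need a displacement limit fixed in advance, and each dropped volume loses 4 s of data. The wording should be settled before unblinding, so that the handling of motion is not chosen with results in view.
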